Study Protocol

Timing Personalized Feedback after Alcohol Health Education

NCT04453007

June 23, 2022

Principal Investigator:

[name].

Description and Purpose of the Project

Heavy episodic alcohol use within the college student population is widespread, creating problems for student drinkers, their peers, and their institutions. Negative consequences from heavy alcohol use can be mild (e.g., hangovers, missed classes), to severe (e.g., assault, even death). Although online interventions targeting college student drinking reduce alcohol consumption and associated problems, they are not as effective as in-person interventions. Online interventions are cost-effective, offer privacy, reduce stigma, and may reach individuals who would otherwise not receive treatment. In a recently completed randomized, controlled trial, an emailed booster with personalized feedback improved the efficacy of a popular online intervention (Braitman & Henson, 2016). A second randomized, controlled trial confirmed efficacy for students of legal drinking age for a longer timeline (Braitman & Lau-Barraco, 2018). Although promising, the booster incorporated in the study needs further empirical refinement. In particular, it is not known if boosters are most efficacious if administered when the intervention effect is still strong, or as the intervention effect begins to wane. Thus, an empirical question is the optimal timing of the second dose.. [Findings from Study 2 should elucidate students' peak receptivity by identifying the delivery timing with the highest efficacy.]

Primary Aims

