The current project seeks to build on past progress by further developing and refining the booster. In particular, to identify the most efficacious timing for sending the feedback. The content will be similar across conditions, but will be disseminated at different times to identify the most impactful timeline. This study compares booster delivery at 2 weeks after the intervention (known to be effective; Braitman & Henson, 2016; Braitman & Lau-Barraco, 2018) to delivery at week 14 (known to be the window when intervention effects wane based on meta-analysis; Carey et al., 2012), and delivery at weeks 6 or 10 (the midpoints between these two empirically-supported times). A fifth group will receive the booster at all four delivery times as a repeated administration comparison. Finally, an intervention-only control group will also be used. Thus, there will be 6 study conditions: those who receive the emailed feedback 2, 6, 10, or 14 weeks after baseline, or at all of those times, or not at all (control). Thus, the aim of the current study is to identify optimal timing for sending the tailored booster feedback via booster email.

Participant population

Eligible participants must 1) have consumed at least 1 drink containing alcohol within 2 weeks prior to participation; 2) be between the ages of 18-24 years old; 3) must be an undergraduate student at the host institution; and 4) [prior to 3/29/21] were enrolled in classes that were in-person or hybrid [had an in-person component] OR [after 3/29/21] have consumed alcohol in person with others in the past 30 days. Note that this last criterion was developed in response to the COVID-19 global pandemic. Attending classes in person was viewed as a proxy for willingness to gather with others in person, potentially drinking with others in person as well. However, study enrollment was slow, and relatively few students were taking classes in person. Thus, we decided to switch to a more direct assessment of social drinking, including enrolling

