Statistical Analysis Plan

Timing Personalized Feedback After Alcohol Health Education (TIME)

NCT04453007

11/13/2020

Statistical Analysis Plan

Prior to hypothesis testing, the data will be examined for normality and outliers. Histograms and values for skewness and kurtosis will be examined. Positively skewed variables will be natural log transformed, unless paired with an excessive number of zeroes. If there are an excess of zeroes in an outcome, the variable will be dichotomized if other values are not well represented, or appropriate modeling techniques will be used (e.g., hurdle models) if other values are well represented. Boxplots will be used to check for outliers. Extreme values will be winsorized (i.e., cases retained in the sample, but values made less extreme). Cases with missing data will be compared to complete cases across major study variables to identify if there are systematic differences in missingness. If significant associations are identified, these variables will be used as covariates in later analyses.

To address the major aim of the study, the data will be analyzed using latent growth models within a structural equation modeling framework. Separate models will be conducted for each alcohol outcome: alcohol consumption (e.g., quantity), and alcohol-related problems. It is not known the exact trajectory across time (baseline, 1 month, 3 months, 6 months, 9 months), so a few models will be compared to identify which best captures the shape of change over time. A simple model that reflects change to 1 month (slope 1; initial change post-intervention) and longer-term maintenance (slope 2; linear growth to 9 months) will be compared to models with additional piecewise slopes or curvilinear components in case longer-term maintenance is not a linear process. Study condition (6 groups) will be dummy coded across 5 variables with “no booster” as the category of reference, and will serve as a predictor of each latent variable (latent intercept, each slope). All models will be conducted using maximum likelihood estimation, and will control for gender. The model for problems will also control for alcohol quantity.

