Given prior findings that emailed booster feedback containing personalized normative feedback and protective behavioral strategies (PBS) was significantly more effective for select groups (i.e., those lower in PBS use [Braitman & Henson, 2016], legal age drinkers [Braitman & Lau-Barraco, 2018]), we will examine potential moderators of booster efficacy as a supplementary exploratory analysis. Legal drinking status by age (coded as 1 = *age 21-24* [legal], 0 = *age 18-20* [underage]) and baseline PBS use (in its original continuous metric) will be explored as potential moderators. For each outcome, two additional models will be conducted (one for each moderator). The moderator will be added as a predictor of each latent factor (latent intercept, slope 1, and slope 2). Multiple interaction terms will be created to capture the interaction with condition (dummy coded across 5 variables). These interaction terms will also be included as predictors of each latent factor. Thus, the outcome at baseline and change over time will be predicted by condition, the moderator, and the interaction between the two, controlling for relevant covariates.

References:

- Braitman, A. L., & Henson, J. M. (2016). Personalized boosters for a computerized intervention targeting college drinking: The influence of protective behavioral strategies. *Journal of American College Health, 64*(7), 509-519.
<http://doi.org/10.1080/07448481.2016.1185725>
- Braitman, A. L., & Lau-Barraco, C. (2018). Personalized boosters after a computerized intervention targeting college drinking: A randomized controlled trial. *Alcoholism: Clinical and Experimental Research, 42*(9), 1735-1747.
<http://doi.org/10.1111/acer.13815>

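### The aim is to identify the best booster timing, but the SAP prespecifies no comparison among the four timings, no quantity or visit to compare them on, and no rule for naming a best one

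*SAP*

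**What the plan says.** The protocol states its purpose twice. Under Description and Purpose of the Project, "an empirical question is the optimal timing of the second dose". Under Primary Aims, "the aim of the current study is to identify optimal timing for sending the tailored booster feedback via booster email". Primary Aims also says that the study compares delivery at week 2 with delivery at weeks 6, 10 and 14.

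The SAP's second paragraph assigns latent growth models to this aim. On condition it says: "Study condition (6 groups) will be dummy coded across 5 variables". The arm that gets no emailed feedback is the comparator for all five, taken "as the category of reference, and will serve as a predictor of each latent variable (latent intercept, each slope"). The starting shape is given as "A simple model that reflects change to 1 month (slope 1; initial change post-intervention"), followed by a second slope that is linear to 9 months. The shape is not fixed: "so a few models will be compared to identify which best captures the shape of change over time", and the simple model "will be compared to models with additional piecewise slopes or curvilinear components in case longer-term maintenance is not a linear process". The third paragraph, on moderators, keeps the same coding: "Multiple interaction terms will be created to capture the interaction with condition (dummy coded across 5 variables").

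Neither document states a contrast or joint test among the four timings, the quantity or visit on which they are compared, or what result would make one timing the best. The power statement in the protocol (under Participant population) concerns detecting the effect of the booster, not differences between timings.

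**The concern.** The trial's one stated question is which timing works best, and the prespecified coefficients answer a different one: whether each arm differs from no booster. The choice of contrast, growth factor and meaning of best can all be settled after the data are seen. With two outcomes, at least two slopes and six pairs of timings, that leaves wide freedom on the main result.

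The nearest available quantities, the slope coefficients, are also awkward for this purpose. Slope 1 covers baseline to 1 month. By then only the week 2 arm and the all-times arm have received a booster. The 3-month visit (about week 13) still precedes the week 14 booster. Each slope taken alone therefore reflects the delivery schedule as well as the booster's efficacy.

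**Working it through.** **Inputs from the documents.** Six conditions; boosters at weeks 2, 6, 10 and 14; assessments at 0, 1, 3, 6 and 9 months; N = 180; 76% retention; β = 0.537; power .80+.

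**Assumptions (not in the documents).** Equal allocation, two-sided 0.05, outcome SD 1, and within-person correlation 0.4, 0.6 or 0.8 under compound symmetry or AR(1) by assessment order. Completers per arm: 180/6 × 0.76 = 22.8.

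**The plan's own figure.** N = 180 can be neither reproduced nor refuted, because the protocol does not say which contrast or growth factor β refers to. Read as an SD difference between one booster arm and control, it gives power 0.44. Read as a fully standardised two-group coefficient, d = 0.537/0.5/√(1 − 0.537²) = 1.27, it gives 0.99. That range spans .80. Below, 0.537 is used as an effect in outcome SDs, for illustration.

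**Step 1: what the slopes return when all timings are equally good.** Give every booster the same lasting benefit of 1 unit from delivery onward. Under compound symmetry the two-slope model fits baseline exactly. Slope 2 is then the least-squares line through months 1, 3, 6 and 9 (mean 4.75, sum of squares 36.75), and slope 1 is that line's value at month 1.
- Week 2: values 1, 1, 1, 1. Slope 2 = 0; slope 1 = 1.00.
- Weeks 6 and 10: values 0, 1, 1, 1. Slope 2 = 3.75/36.75 = 0.10; slope 1 = 0.75 − 3.75 × 0.102 = 0.37.
- Week 14: values 0, 0, 1, 1. Slope 2 = 5.5/36.75 = 0.15; slope 1 = 0.50 − 3.75 × 0.150 = −0.06.

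The arms are identical at 6 and 9 months, yet in expectation slope 1 puts week 2 first and slope 2 puts week 14 first.

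**Step 2: how often equal timings would be called different.** For a slope with arm means m and per-person variance v, λ = Σ(m − m̄)²/(v/22.8), and rejection is the noncentral chi-square probability on 3 df. Example at compound symmetry 0.4:
- Slope 1: v = 0.6 × (1 + 1/4 + 3.75²/36.75) = 0.980; Σ(m − m̄)² = 0.537² × 0.573 = 0.165; λ = 3.85; rejection 35%.
- Slope 2: v = 0.6/36.75 = 0.0163; Σ(m − m̄)² = 0.537² × 0.0119 = 0.00344; λ = 4.81; rejection 42%.

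Over all the assumed correlations:

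| Quantity (lasting 0.537 SD, equal timings) | 3-df test rejects | Ranked first |
|---|---|---|
| Slope 1 | 32-83% | week 2 in 79-99% |
| Slope 2 | 24-91% | week 14 in 49-80% |
| Fair comparison | 5% | each in 25% |

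**Step 3: quantities that do work.** With one slope per interval, summed to 6 or 9 months, every arm has the same expected value and the test rejects in 5%. Change implied by the two-slope model is in between. In Step 1 it gives 0.37 + 8 × 0.102 = 1.18 (weeks 6 and 10) and −0.06 + 8 × 0.150 = 1.14 (week 14) at 9 months, against a true 1.00. Rejection is 7-15% at 6 months and 5-8% at 9 months at 0.537 SD. At 1.074 SD (2 × β) it is 16-51% and 5.5-17%.

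**Step 4: power for a real timing difference at N = 180.** Let one timing differ from the other three by 0.537 SD. Then λ = 22.8 × 0.537² × 0.75/v = 4.93/v, with error df 6 × 22.8 − 6 = 130.8. The variance v is 1 − ρ² with baseline adjustment and 2(1 − ρ) for unadjusted change, where ρ is the baseline-to-follow-up correlation. It runs from 0.4⁴ = 0.026 (AR(1) at 9 months) to 0.8.

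| Analysis | 3-df test | One timing beats all three others (Tukey, simulated) |
|---|---|---|
| Baseline-adjusted | 42-88% | 6-42% |
| Unadjusted change | 23-84% | 2-36% |

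**The case against.** The strongest reply is that nothing in the plan prevents the right analysis. The five dummies span every difference between timings, so any contrast can be formed from the fitted model. The SAP allows additional piecewise slopes, and with one slope per interval the summed slopes recover the correct comparison. Even change implied by the two-slope model is only mildly distorted at 9 months when the effect is 0.537 SD. The protocol also states a criterion, the timing with the highest efficacy.

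Most of this stands, and it limits the point. A reader might infer that the coding makes timing comparisons impossible or that the slopes are unusable; neither is true. A reader might also infer that the SAP intends to rank timings on one slope, or by which arms reach significance against no booster. It says neither, so the rates in Step 2 describe what would follow from a natural reading of the coefficients, not a stated procedure. They also depend on assumed correlations and on a lasting effect.

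What the reply does not remove is the gap itself. The highest-efficacy criterion has no metric, visit or test. The combination of slopes that would be fair is not prespecified, and whether the model is flexible enough to provide it depends on a shape comparison made on the data.

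**Conclusion.** The concern holds as a failure of prespecification on the trial's main question, and it needs correcting. The SAP names no timing contrast or joint test, no comparison quantity or visit, and no rule for a best timing. The coefficients that it does name are not a fair basis if read one slope at a time. Under equally effective lasting boosters of 0.537 SD they would show false timing differences in 32-83% (slope 1) or 24-91% (slope 2) of trials, with opposite timings tending to come first. These sizes rest on 22.8 completers per arm, equal allocation, two-sided 0.05 and correlations of 0.4-0.8, none of which the SAP states. The omission does not depend on them.

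The documents do not support the further inference that N = 180 is wrong for its stated purpose, because β is not defined. They show only that the stated power is not power for timing differences.

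**What to change.** Amend the SAP as follows.

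1. **Quantity.** Compare the four single-timing arms on the baseline-adjusted outcome at one named follow-up after all boosters (6 or 9 months, the investigators' choice, fixed before data are seen). Leave condition means free at each post-baseline assessment, with a common baseline mean or baseline as a covariate. Keep the gender covariate, and say whether the alcohol-quantity covariate of the problems model applies here. If the outcome is transformed, dichotomised or hurdle-modelled, state the contrast on that scale. Keep the growth model to describe trajectories.
2. **Test and rule.** Test equality of the four arms with a 3-df Wald test. Report multiplicity-adjusted pairwise differences with confidence intervals. Base any claim of a best timing only on these contrasts, not on significance against no booster. State whether consumption or problems decides, or report a separate conclusion for each.
3. **Power.** State that the protocol's .80+ refers to the effect of the booster. Give power for timing differences under stated assumptions, both for the 3-df test and for any rule that one timing must beat the other three. Say that non-rejection does not show equivalence.

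The cost is SAP wording, one extra model specification and a few constraint lines, with no new data. There are two downsides. An inconclusive timing result is likely at N = 180. Also, if effects decay, a fixed visit mixes timing with time since the booster, which the SAP should state. For example, with an assumed half-life of 13 weeks, equally effective boosters retain 0.5^(24/13) = 0.28 of their effect at 6 months if sent at week 2, and 0.5^(12/13) = 0.53 if sent at week 14.

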online students in the study if they reported drinking alcohol with others in person. Power analyses were conducted using Monte Carlo simulation methods within Mplus (version 5.21, Muthén & Muthén). Effect sizes, variance, and covariances used were based on data from a preliminary study with similar eligibility criteria using the same booster content (Braitman & Henson, 2016; Braitman & Lau-Barraco, 2018). We estimated a retention rate of 76%, the average reported in a meta-analysis of RCTs assessing alcohol interventions for first-year college students (Scott-Sheldon et al., 2014). Monte Carlo simulation methods indicated that for the effect size expected ($b = 6.57$, $\beta = 0.537$) and for the expected 24% attrition, a sample size of $N = 180$ total students should yield sufficient power (.80+) to detect booster effects.

Recruitment Procedure

An email describing the study is sent to undergraduate students at ODU ages 18-24 who have enrolled in at least 1 credit hour, and includes a link to a screener survey. In addition to eligibility criteria (age, student status, if they drink with others, and alcohol consumed) additional irrelevant questions are included in the screener survey to discourage ineligible participants from re-taking the screener survey with different answers. Eligible participants can provide their contact information (name, email, and phone number) and are linked to Calendly to schedule their participation in the baseline protocol via Zoom.

Study Procedure

Emerging adult college drinkers are recruited via email as described above. After completing the screener to verify eligibility, participants schedule their participation time through an online time management system (Calendly). They receive an email reminder from the Calendly system 24 hours before their assigned timeslot. After participating in the fully remote baseline session via Zoom, participants are be paid \$20. They are also be invited to complete follow-up surveys for additional money. Participants are invited to complete 1-, 3-, 6-, and 9-month assessments, and receive \$10 for each completed follow-up survey. As an additional incentive, participants who complete all assessments will be given a \$10 bonus (yielding a \$70 total for the study if all follow-ups are completed). All monetary compensation is provided via online gift card to Amazon.

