Baseline: Participants sign on to Zoom via the link provided during their assigned timeslot. Upon signing into the Zoom meeting, the research assistants provide a link (using the chat function) directing them to a Qualtrics survey. Participants read and view videos of the study procedures on the first page of this website. The videos have been created in Powtoon, using voiceover and images that are not related to a specific gender or race/ethnicity. After reviewing the videos, participants are provided with the informed consent document (on a subsequent page of the survey), will have the opportunity to ask questions during the live Zoom session with the research assistant. After consenting to participate, they are directed to complete the baseline survey (approximately 30-45 minutes). All participants will complete this computerized survey that assesses alcohol use, alcohol-related problems, protective behavioral strategies for drinking and their perceived effectiveness, motives and expectancies for alcohol use, anonymized social network characteristics, context of their most recent drinking occasion, marijuana and tobacco use, COVID-19 experiences, internalizing symptoms, and demographic

measures. Through a mechanism of the survey, participants are randomly assigned to one of six possible conditions regarding the timing of receiving emailed personalized feedback about their alcohol use. After completing the initial assessment, participants are then be directed to navigate through the eCHECKUP TO GO program (San Diego State University Research Foundation, 2018) until it is completed (approximately 20-30 minutes).

Subsequent assessments: Approximately 1, 3, 6, and 9 months after the initial assessment, researchers send each participant an email reminding them to complete the follow-up assessment. This email includes a link to an online follow-up survey that assesses alcohol use, related problems, protective behavioral strategies for drinking and their perceived effectiveness, anonymized social network characteristics, context of their most recent drinking occasion, and marijuana and tobacco use. If participants provide additional ways to contact them during the baseline survey (a second email address, a phone number to text), these methods are also used to send the link to the follow-up surveys.

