Boosters: After the intervention, participants receive an additional email from the researcher, depending on their study condition. For five study conditions, these emails contain personalized normative feedback about alcohol use as well as feedback about harm reduction strategies, serving as a booster to the original intervention. Baseline data are used to provide students with normative information (e.g., typical drinking among ODU students who are male/female depending on the gender of the recipient), and reminders of protective behavioral strategies they can use to reduce drinking-related harm (separated by strategies they have reported using recently versus those they might consider trying). This is received at 2 weeks, 6 weeks, 10 weeks, or 14 weeks after baseline for study conditions 1-4 respectively. This is received at all of those times for some participations (the 5th study condition). Participants in the control condition (6th study condition) do not receive any feedback via email.

Measures

The same measures are included in baseline and the follow-up surveys:

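### Precision left unused, not an error: arms are randomised at baseline, yet the SAP estimates five condition effects on the latent intercept that are zero in expectation

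*SAP*

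**What the plan says.** The SAP's second paragraph codes the six conditions as five dummies with no booster as reference. These dummies "will serve as a predictor of each latent variable (latent intercept, each slope"). The paragraph on moderators repeats the choice, so it is deliberate: "the outcome at baseline and change over time will be predicted by condition, the moderator, and the interaction between the two". The simplest growth shape is described as "A simple model that reflects change to 1 month (slope 1; initial change post-intervention") plus a second slope for linear growth to 9 months. Estimation is by maximum likelihood, controlling for gender; the problems model also controls for alcohol quantity.

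The protocol fixes the order of events. During the baseline survey "participants are randomly assigned to one of six possible conditions regarding the timing of receiving emailed personalized feedback". The online programme comes next: "After completing the initial assessment, participants are then be directed to navigate through the eCHECKUP TO GO program". The arms then differ only in emails: "This is received at 2 weeks, 6 weeks, 10 weeks, or 14 weeks after baseline for study conditions 1-4 respectively", with a fifth arm emailed at all four times and a control arm not emailed.

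On sample size, the protocol plans N = 180 in total with 24% attrition and states: "Effect sizes, variance, and covariances used were based on data from a preliminary study". The values themselves are not printed.

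**The concern.** With free intercepts, each arm's change is measured from that arm's own observed baseline. At 180/6 = 30 per arm (equal allocation assumed) that mean is noisy, and its error passes into every change contrast. Because the arms are randomised and treated alike until week 2, their true baseline means are equal in expectation. The model therefore spends five parameters per outcome on quantities the design already sets to zero. A common baseline mean is the growth-model counterpart of baseline adjustment, and it uses data already collected. With 30 x 0.76 = about 23 per arm expected at the end of follow-up, the lost precision could matter for single-arm contrasts.

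**Working it through.** **The plan's own figure.** N = 180 for power of .80 or more cannot be reproduced. The covariances, the tested parameter and the significance level are not given. The figure is neither confirmed nor refuted, and nothing below depends on it beyond the number per arm.

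**Inputs from the documents.** Six arms, N = 180, visits at 0, 1, 3, 6 and 9 months, 24% attrition.

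**Assumed inputs.**
- Equal allocation and a continuous outcome.
- Loadings: intercept (1,1,1,1,1), slope 1 (0,1,1,1,1), slope 2 (0,0,2,5,8).
- Growth-model covariances: variances 0.6 (intercept), 0.15 (slope 1), 0.004 (slope 2) and 0.35 (residual), with each intercept-slope correlation at -0.3, 0 or +0.3 (nine combinations).
- Compound symmetry with correlation 0.5, 0.6 or 0.7.
- Attrition monotone, 6% at each follow-up; everyone has a baseline.

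**Formula.** Let b be the regression of the model-implied follow-up level on the baseline measurement. A common baseline lowers the variance of an arm-versus-control change by

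(1 - b)² x 2 x (baseline variance) / (n per arm).

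**Slope 1, zero correlations, complete data.** Baseline variance is 0.6 + 0.35 = 0.95, and b = 0.6/0.95 = 0.632. The saving is 0.368² x 2 x 0.95/30 = 0.0086. The variance falls from 0.0481 to 0.0395: SE 0.219 to 0.199, ratio 0.82.

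**Change to 9 months, complete data.** The intercept-slope covariances are ±0.3 x √(0.6 x 0.15) = ±0.09 for slope 1 and ±0.3 x √(0.6 x 0.004) = ±0.0147 per month for slope 2. The free-intercept variance is 0.0677.
- Both correlations -0.3: b = (0.6 - 0.09 - 8 x 0.0147)/0.95 = 0.41, saving 0.0218, ratio 0.68.
- Both correlations +0.3: b = (0.6 + 0.09 + 8 x 0.0147)/0.95 = 0.85, saving 0.0014, ratio 0.98.

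**Slope 2, complete data.** It gains only if the covariance with baseline drifts after month 1. A drift of 0.0147 per month gives a ratio of 0.983; no drift gives 1.000.

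**Variance ratios, common baseline divided by free intercept, over the twelve structures:**

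| Contrast | Complete data | 24% attrition |
|---|---|---|
| Slope 1 | 0.69-0.90 | 0.71-0.91 |
| Change to 6 months | 0.60-0.95 | 0.64-0.95 |
| Change to 9 months | 0.68-0.98 | 0.72-0.98 |
| Slope 2 | 0.98-1.00 | 0.99-1.00 |

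**Wider range.** Over 900 growth-model covariances with 24% attrition, slope 1 runs 0.59-1.00 (median 0.82), 9-month change 0.52-1.00 (median 0.89) and slope 2 0.90-1.00 (median 0.99). A gain of nil is therefore possible. Autoregressive covariances give larger gains at 6 and 9 months and on slope 2, but the SAP's growth model does not specify them.

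**Power.** For an assumed effect of 0.5 baseline SD, two-sided 0.05, 24% attrition and both correlations at -0.3, 0 or +0.3, slope 1 power moves from 57-58% to 62-71%, and 9-month power from 40-41% to 41-53%.

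**Estimated covariances.** In simulation (1,000 trials per scenario, N = 180, maximum likelihood) the slope 1 ratios were 0.74, 0.84 and 0.93, and the slope 2 ratios 1.00, 1.01 and 0.99. Type I error was 0.048-0.065 with free paths and 0.053-0.067 with the constraint (Monte Carlo SE about 0.007).

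**Downside.** If one analysed arm truly differs at baseline, a share (1 - b) of that difference enters its effect. For a 0.2 SD difference, slope 1 picks up 0.2 x (1 - 0.69/0.95) = 0.055 SD up to 0.2 x (1 - 0.5) = 0.10 SD. The 9-month change picks up 0.2 x 0.15 = 0.03 SD up to 0.2 x 0.59 = 0.12 SD. The free-intercept model has no such bias.

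**The case against.** The planned model is a legitimate choice, stated twice. A reader might infer that free intercepts bias the slope contrasts or make the analysis wrong; they do not.

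A reader might also infer that the constraint strengthens the timing comparison throughout. It does not. Slope 1 precision rises equally in every arm, but at month 1 only the 2-week and all-times arms have been sent a booster. For the 6-, 10- and 14-week arms slope 1 is a pre-booster contrast, and slope 2, where their effect would have to show, gains almost nothing. Those arms benefit only through change to 6 or 9 months, which the SAP does not name as a contrast.

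Testing those changes formally would add 5 arms x 2 times x 2 outcomes = 20 contrasts to the existing 5 x 2 slopes x 2 outcomes = 20. Under Bonferroni (an assumption; the SAP states no control), a slope 2 contrast with 80% power at 0.05 would have about 41% with 20 tests and 34% with 40. That objection stands, so such changes should be descriptive.

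Three limits also stand:
- The figures assume a continuous or logged outcome and do not carry over to the SAP's dichotomised or hurdle options.
- They omit the quantity covariate in the problems model.
- The SAP is dated 11/13/2020 and the June 2022 protocol describes enrolment under way, so a late change to the primary model could cost credibility. The documents do not say whether outcomes have been examined by arm.

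One could ask for the gain to be computed from the preliminary-study covariances first. That would be informative, but there is no natural threshold for acting on it, and large-sample precision is never worse under the constraint.

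**Conclusion.** The point holds as an inexpensive improvement of low priority. For continuous or logged outcomes, with 24% attrition and the assumed covariances, the constraint cuts the variance of an arm-versus-control contrast by about 9-29% on slope 1, 2-28% on change to 9 months and 0-1% on slope 2. The true gain may be near zero. That the constraint never loses precision is a large-sample result; with estimated covariances a negligible loss on slope 2 is possible. Its validity requires the analysed arms to be the randomised arms. No gain is established for dichotomised or hurdle outcomes, or for the problems model with its quantity covariate.

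**What to change.** Before outcomes are examined by arm, amend the SAP as follows.

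- In the primary models of continuous outcomes, for growth shapes whose intercept is the baseline mean, fix the five condition-to-intercept paths to zero. Keep gender and other covariates on the intercept, leave the intercept-slope covariances free, and include every randomised participant with a baseline.
- Keep the free-intercept model as a prespecified sensitivity analysis. It guards against exclusions after randomisation that make the analysed arms differ at baseline.
- In the exploratory moderator models, treat the condition and condition-by-moderator paths to the intercept in the same way, and keep the moderator's own path.
- Report any model-implied change to 6 and 9 months by arm as descriptive estimates with confidence intervals, not as 20 added tests.

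The cost is SAP wording, model syntax and one extra model fit per outcome; no new data are needed. The amendment should be dated and should state whether any outcome data had been seen by arm.
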